9.2.1 Inclusion criteria

The survey will be conducted among physicians meeting the following inclusion criteria:

• Prescribers of Intuniv[®], i.e. physicians who know and have prescribed the drug at least once during the previous 12 months (or, for the first report, since country specific launch) (paediatricians, psychiatrists, neurologists and GPs)

9.2.2 Exclusion criteria

Inactive and retired physicians (when documented information is available to identify them) will be deleted from the contact lists before randomisation.

The following exclusion criteria will be checked at the beginning of the webquestionnaire:

• Physicians who do not treat patients or who may have a conflict of interest (i.e. physicians employed by regulatory bodies or pharmaceutical industries),

9.3 VARIABLES

The survey aims to characterize patients who are prescribed Intuniv[®] and describe prescribing patterns of Intuniv[®] among physicians in European countries.

The following information is planned to be collected in the survey:

- Physician related data
 - o demographics
 - o setting
 - o prescriber's specialty
- patient characteristics
 - o age
 - o gender
 - o co-morbidities
- indication of use (diagnosis) according to WHO ICD 10 classification
- data on patterns of drug use
 - o first time user
 - o repeat user
 - o duration of treatment
 - o discontinuation of ADHD therapy
 - o switches (both from Intuniv[®] to other ADHD medications and other ADHD medications to Intuniv[®])
 - o dosing/ overdose (defined as daily dose of >7 mg or of >4mg in patients ≤12 years of age)
- use of Intuniv[®] as second line treatment after psychostimulant prescription at any time prior to the patient's first prescription of Intuniv[®]
- frequency of monitoring (physician) visits during the first year of therapy
- weight, blood pressure and heart rate during Intuniv[®] exposure

A detailed description of all variables and definitions is provided in Table 3 of the SAP for the survey protocol.

9.4 DATA SOURCES

Physician Survey

• de-identified patient data provided by a representative sample of physicians known to treat patients with ADHD – predominantly paediatricians, psychiatrists, neurologists and general practitioners (GPs), representatively selected throughout the respective countries. The physicians will be instructed to select the patient record based on the last patient they have seen, for whom at any time in the last 12 months (or, for the first report, since country specific launch) they have prescribed Intuniv® (whether or not Intuniv® was prescribed at that last visit).

The survey will collect data from the following sources:

- physicians files (OneKey lists)
- information collected by a web questionnaire, including de-identified patient data

The questionnaire will be designed by experienced persons and will include both open and close-ended questions. Several questions directed to the physicians concerning their knowledge about the risk minimization measures and the educational material will be included. The web questionnaire completion is estimated to take 5 to 10 minutes for the general part and an additional 10 minutes per patient for the drug utilization data. Before being finalized, the questionnaire will be administered to/ tested by 5-6 physicians in order to make sure it is well understood and the wording appropriate to the survey topic. Physicians' comments will be implemented in the final version. Moreover, the questionnaire will be translated using the back and forth method (translation from English to local language, then again to English) to make sure the appropriate wording is used.

9.5 STUDY SIZE

9.5.1 **Sampling plan**

Per country and year, the target is to collect data from 50 to 100 patients, who have been prescribed Intuniv[®] at least once during the study period, provided by representative physicians qualified to treat patients with ADHD. It is planned to annually recruit 15 to 20 prescribers of Intuniv[®] per country who will be requested to complete, if possible, 1 to 10 medical record extracts.

A random sampling plan will be developed. Prescribers will be sampled among the lists of paediatricians, GPs, neurologists and psychiatrists.

Due to the low prescribing base, no quotas by physician types will be set. As many patient medical records (anticipated maximum: 100 records per country) from as many prescribing physicians who are willing to participate will be collected.

9.5.2 Study size calculation

As the expected number of patients receiving Intuniv[®] is expected to be very low, descriptive statistics will be applied. It is planned to collect, if possible, data for up to 100 patients per country, who have been prescribed Intuniv[®] at least once during the study period. Data will be provided by representative physicians qualified to treat patients with ADHD.

The exact number of prescriptions/ patient records to be analyzed will depend significantly on the market utilization of Intuniv[®] in the target countries.

The planned sample size of at least 100 patients was determined as described here:

The sample size formula, based on the normal approximation to the binomial distribution, for calculation of the number of subjects n required to determine a proportion p with a precision e with a two-sided α first-type error is the following:

$$n = \frac{p \times (1-p) \times z_{1-\alpha/2}^2}{e^2} (1)$$

Based on this sample, and considering a confidence interval of 95%, in order to be able to determine any percentage with a precision of at least $\pm 5\%$, 384 subjects will be necessary. This corresponds to a hypothetical proportion of 50% which is generally considered as it yields to the largest sample size for each precision level. Respectively, a precision of at least $\pm 10\%$ would necessitate a sample size of 97 subjects.

In this study, assuming that we would like to be able to describe any proportion with a precision of at least 10% in each country, a minimum sample size of 100 cases per year is required for any of the countries. In the case this figure is not reached for the annual analyses of a target country IQVIA and Shire will discuss and mutually agree on alternative options (for example analyses of smaller sample sizes or postponement the analysis to the subsequent year in order to reach a bigger sample size).

Prior to the analysis each year, actual numbers of available prescriptions will be checked to decide if the analysis will be feasible.

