9.7.3 Questionnaire analysis

The reports will include descriptive statistics of all parameters analyzed. As part of this analysis, the description of missing data for each outcome of interest will be provided. Missing values are expected to be few and distributed at random. Since there is no applicable method unanimously accepted, there will be no replacement or imputation of missing data (17).

For continuous variables the number of non-missing observations, mean, standard deviation, median, minimum and maximum will be presented.

Categorical data will be summarized using frequency and percentage. 95% confidence interval may be constructed around the percentage values for some variables. Some of the variables may also be summarized by country.

The educational materials will be considered to be effective if at least 80% of physicians will have responded correctly to at least 75% of the questions in the survey in which knowledge on the educational material is assessed.

This hypothesis is based on empirical numbers.

Evaluation of the success rate will be based on the percentage of correct answers to questions A2 to A5 in Section 4 ("Awareness and knowledge of risk minimisation measures") of the survey questionnaire.

Two analyses to evaluate the effectiveness of the risk minimization measures will be performed:

In the main analysis all questionnaires will be evaluated. In the subgroup analysis, only questionnaires of the physicians who answered "Yes" to question A7 ("Did you receive educational material regarding Intuniv[®]?") will be included. The subanalysis will allow to evaluate if awareness of the educational material may affect the number of correct answers.

More detailed information regarding the evaluation of the effectiveness is given in the survey SAP.

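### The ±10-point per-country precision in 9.5.2 assumes independent patients, but the 100 records are to come from 15 to 20 physicians, so it holds only if within-physician correlation is almost nil

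*Protocol*

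**What the plan says.** Protocol 9.5.2 introduces the calculation as "The sample size formula, based on the normal approximation to the binomial distribution", "considering a confidence interval of 95" per cent. It takes the worst case: "This corresponds to a hypothetical proportion of 50" per cent. A precision of ±10% then "would necessitate a sample size of 97 subjects", and this becomes a required minimum of 100 cases per country and year, "assuming that we would like to be able to describe any proportion with a precision of at least 10% in each country".

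Protocol 9.5.1 describes how the records arise. "It is planned to annually recruit 15 to 20 prescribers of" the product in each country, "who will be requested to complete, if possible, 1 to 10 medical record extracts". The target is 50 to 100 records per country and year, with an anticipated maximum of 100. Section 9.2 confirms the 1 to 10 records per physician, most recent patients first.

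On intervals, 9.7.3 says only that a "95% confidence interval may be constructed around the percentage values for some variables". Sections 9.5, 9.7 and 9.9 do not mention clustering within physician, an intracluster correlation or a design effect.

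**The concern.** The size formula treats every patient record as an independent draw. The sampling plan does not produce independent draws: physicians are sampled from lists, and patients enter only through them, several at a time. That is a cluster sample sized as a simple random sample.

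A positive correlation within physician is plausible here. The primary objectives in 8.2 concern indication, age group, absence of prior stimulant treatment and dose. Each reflects either a prescriber's decision or the kind of practice. Physicians come from four specialties without quotas, so age and indication may also cluster by specialty.

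At stake is the stated precision of the per-country percentages, which are the primary output of each annual report. Precision is the only formal argument that 9.5.2 gives for the figure of 100.

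**Working it through.** **Inputs from the protocol.** p = 0.50, two-sided 95% (z = 1.960), e = 0.10, N = 100 records per country and year (9.5.2); k = 15 to 20 physicians, 1 to 10 records each (9.5.1).

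**Assumption.** The ICC is not in the protocol. It is shown over 0.02 to 0.30.

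**1. The plan's own figures.** n = p(1 − p)z²/e².
- e = 0.10: 0.25 × 1.960² / 0.01 = 96.04, rounded up to 97, as stated.
- e = 0.05: 0.25 × 1.960² / 0.0025 = 384.1, stated as 384.

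The arithmetic is right under independence. At N = 100 the independent half-width is 1.960 × √(0.25/100) = 9.8 points.

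**2. Room for clustering.** The largest design effect that keeps ±10 points is 100/96.04 = 1.041. With DE = 1 + (m − 1) × ICC and m = N/k:
- 20 physicians, m = 5: ICC ≤ 0.041/4 = 0.010.
- 15 physicians, m = 6.67: ICC ≤ 0.041/5.67 = 0.007.

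**3. Half-width at 100 records and p = 50%.** Half-width = 1.960 × √(0.25 × DE/100); effective n = 100/DE.

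| ICC (assumed) | 20 physicians: DE, effective n, half-width | 15 physicians: DE, effective n, half-width |
|---|---|---|
| 0.02 | 1.08, 93, ±10.2 | 1.11, 90, ±10.3 |
| 0.05 | 1.20, 83, ±10.7 | 1.28, 78, ±11.1 |
| 0.10 | 1.40, 71, ±11.6 | 1.57, 64, ±12.3 |
| 0.20 | 1.80, 56, ±13.1 | 2.13, 47, ±14.3 |
| 0.30 | 2.20, 45, ±14.5 | 2.70, 37, ±16.1 |

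The table assumes equal record counts. Unequal counts widen it. If 20 physicians gave 10, 7, 2 and 1 records in groups of five, m is replaced by Σm²/Σm = 770/100 = 7.7. At ICC 0.10, DE = 1 + 6.7 × 0.10 = 1.67 and the half-width is ±12.7.

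**4. Lower proportions.** Half-width = 1.960 × √(p(1 − p) × DE/100).
- p = 20%, ICC 0.10: ±9.3 (20 physicians) to ±9.8 (15 physicians).
- p = 10%, ICC 0.10, 20 physicians: ±7.0.
- p = 10%, ICC 0.30, 15 physicians: ±9.7.
- p = 5%, ICC 0.30, 15 physicians: ±7.0.

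**5. What holding ±10 points at 50% would take.** At the planned records per physician, 96.04 × DE gives 116 to 124 records (ICC 0.05), 135 to 151 (ICC 0.10) or 173 to 205 (ICC 0.20), all above the anticipated maximum of 100. At 100 records, m could be at most 1 + 0.041/ICC. That means about 55 physicians at ICC 0.05 and about 71 at ICC 0.10.

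**6. Coverage, if ordinary binomial intervals were used.** Approximate coverage is 2Φ(1.960/√DE) − 1. From ICC 0.05 with 20 physicians to ICC 0.30 with 15 physicians, it falls from 93% to 77%. A beta-binomial simulation of the Wald interval (p = 50%, 100 records, 20,000 runs per setting) gives slightly lower values, from 92% down to 75%.

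**The case against.** Several points on the other side are sound.

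- **No decision depends on ±10 points.** The study is descriptive, and 4.9 and 9.7.1 rule out statistical comparison. The one pre-set threshold, in 9.7.3, is scored per physician, so clustering of patients does not affect it. This stands and limits the severity.
- **Feasibility largely sets the size.** Section 9.5.2 says that the number of records depends on market use and provides for a shortfall. Section 9.5.1 would take more willing physicians, so 15 to 20 is a plan and not a cap. This stands too, but recruitment stops once the target is reached (9.6.1), and the precision statement remains in the text.
- **The loss may be small.** At ICC 0.02 to 0.05 the half-width is ±10.2 to ±11.1. If most categories of interest are uncommon, which is an assumption because the protocol gives no rates, they keep an absolute half-width below 10 points. That is correct. However, 9.5.2 makes its statement for every proportion and itself chose 50%, and absence of prior stimulant treatment could be mid-range.
- **A finite-population correction could recover some precision** if nearly all users were sampled. The protocol gives no count of users and applies no such correction.

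A reader might also infer that the reported 95% intervals will be too narrow. The protocol does not support that. Section 9.7.3 makes intervals optional and names no method, and the SAP, which is not at hand, may specify a clustered one. The coverage figures apply only if ordinary binomial intervals are used.

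**Conclusion.** The concern holds for the precision statement in 9.5.2. The calculation is correct for independent patients but does not describe the sample planned in 9.5.1. At 100 records and 50%, independence already uses 9.8 of the 10 points, so the stated precision is lost once the ICC passes about 0.007 (15 physicians) to 0.010 (20 physicians). This conclusion therefore does not need a high ICC. The size of the loss does depend on the ICC: ±10.2 to ±16.1 points over the assumed 0.02 to 0.30, with equal record counts and no finite-population correction. The failure is mainly for mid-range proportions.

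This is a should-fix point. It concerns an assumption rather than an arithmetic error, in a descriptive study where nothing is triggered by ±10 points.

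A separate matter should not be mixed with this one. At 50 records, the lower end of the target, the half-width is 1.960 × √(0.25/50) = ±13.9 points even without clustering.

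**What to change.** **In 9.5.2:** add DE = 1 + (m − 1) × ICC, with m taken from the planned records per physician, and replace the single ±10% with a range over plausible ICCs. For example, at 100 records and 50%: about ±10.7 to ±11.1 at ICC 0.05, ±11.6 to ±12.3 at 0.10, and ±13.1 to ±14.3 at 0.20. State that the ICC is assumed, and add a line for a low proportion such as 10%.

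**In 9.7.3:** state that any 95% interval presented for a patient-level proportion treats the physician as the cluster, unless the SAP already says so. Whether and for which variables intervals are shown can stay as it is.

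**Cost:** two wording changes and, if the SAP does not yet allow for clustering, a clustered variance in place of a binomial one. No more patients are enrolled. The stated precision becomes less favourable.

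### The plan requires at least 100 records per country and year for ±10 points, yet counts 50 to 100 as on target and leaves any shortfall to an annual agreement

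*Protocol*

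**What the plan says.** Protocol 9.5.2 gives the formula for estimating a proportion "with a precision e with a two-sided α first-type error", takes 95% confidence and a worst-case proportion of 50%, and obtains 384 subjects for ±5% and 97 for ±10%. Its aim is to "describe any proportion with a precision of at least 10% in each country", and it concludes that "a minimum sample size of 100 cases per year is required for any of the countries". It also calls the planned size at least 100.

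Other statements on size differ:

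- Earlier in 9.5.2, data are planned for up to 100 patients per country, if possible.
- In 9.5.1, "the target is to collect data from 50 to 100 patients" per country and year, with "anticipated maximum: 100 records per country". Sections 4.8 and 9.2 repeat the 50 to 100 range.
- In 9.6.1, recruitment in a country stops when the target is reached, without saying whether that is 50 or 100.

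If 100 is not reached, 9.5.2 says that "IQVIA and Shire will discuss and mutually agree on alternative options". Its two examples are analysing a smaller sample and postponing the analysis to the following year. A further sentence has feasibility decided each year from the available numbers, with no threshold. Section 6 promises annual results for each of the four survey countries, and Table 2 marks each of them for 2019, 2020, 2021 and 2022.

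**The concern.** One number serves as the required floor and as the expected ceiling, while half of it counts as on target. A team could stop at 50 records, comply with 9.5.1 and 9.6.1, and still breach 9.5.2. A reader of 9.5.2 would expect ±10 points in every country and year, which most of the target range does not deliver.

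The second issue is what happens on a shortfall. Section 9.5.2 expects very few treated patients and 9.5.1 refers to a low prescribing base, so counts below 100 are foreseeable. For these the protocol fixes no rule. It leaves the choice to the contractor and the sponsor each year, and one named option is that a country's results do not appear on schedule. This is a risk-management study that evaluates the sponsor's own educational materials, so whether a country is reported on time should be settled in advance.

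**Working it through.** **Inputs (Protocol 9.5.1 and 9.5.2).** 95% confidence, two-sided, z = 1.96; worst-case p = 0.50; required precision e = 0.10; target 50 to 100 records; 15 to 20 physicians per country and year; 1 to 10 records each.

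**1. The plan's own figures.** n = p(1−p)z²/e².

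- e = 0.10: 0.25 × 1.96² / 0.01 = 96.04, rounded up to 97.
- e = 0.05: 0.25 × 1.96² / 0.0025 = 384.1, stated as 384.

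Both reproduce (strict rounding up would give 385 for the second, which is immaterial).

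**2. Precision across the target range.** Half-width = 1.96 × √(0.25/n).

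| Records | Worst-case 95% half-width |
|---|---|
| 50 | ±13.9 points |
| 75 | ±11.3 points |
| 96 | ±10.002 points |
| 97 | ±9.95 points |
| 100 | ±9.8 points |

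Of the 51 whole numbers from 50 to 100, only four (97 to 100) meet ±10 for any proportion. The shortfall clause is tied to 100, so it is triggered by 50 of the 51 (50 to 99).

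**3. Where ±10 still holds at 50 records.** It needs p(1−p) ≤ 50 × 0.01 / 1.96² = 0.130, that is, p up to about 15% or from about 85%.

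**4. Rare categories.** With zero events the exact two-sided 95% upper limit is 1 − 0.025^(1/n): 7.1% at n = 50 and 3.6% at n = 100. These limits matter if the off-label categories in the primary objective are rare; the protocol gives no expected frequencies.

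**5. Clustering.** The formula treats records as independent, although a physician may supply up to 10. Reaching 100 records takes 100/20 = 5.0 to 100/15 = 6.7 per physician. The protocol gives no intraclass correlation. Assuming 0.05 to 0.20, the design effect 1 + (m − 1) × ICC runs from 1 + 4.0 × 0.05 = 1.20 to 1 + 5.67 × 0.20 = 2.13. The half-width at 100 records is then 9.8 × √1.20 = ±10.7 to 9.8 × √2.13 = ±14.3 points. Under that assumption even 100 records would miss ±10. The main point does not depend on it.

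**6. Postponement against the reporting schedule.** Section 6 and Table 2 have every survey country in every annual report. Fieldwork ends on 31 March 2022 and the last report is due on 30 June 2022, so a shortfall in 2022 has no following survey to move to.

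**The case against.** The strongest reply is that the study is descriptive, with no statistical comparison (4.9, 9.7.1). The ±10 is worded as a wish, 9.5.2 openly says that numbers will be low and depend on market use, and no test or power rests on 100 records. The 80% criterion for the educational materials in 9.7.3 is scored on physicians, not on patient records. All of this stands, and it limits the severity. It does not remove the conflict between a required minimum of 100 and a target that starts at 50.

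Several stronger readings are tempting, and the protocol does not support them:

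- **An arithmetic error in 9.5.2.** There is none. The fault lies in how the result is used.
- **A precision missed by design.** At 97 to 100 records ±10 is just met before clustering, and 100 is an anticipated maximum, not a hard cap.
- **Loss of ±10 for every proportion below 97 records.** The failure is for the worst case, which counts because the protocol claims any proportion. Step 3 shows where ±10 survives.
- **A route for holding back unfavourable results.** The trigger is a record count checked before analysis, and nothing links it to findings. Analysing a smaller sample is the first example given. That the clause will become the usual route is a reasonable forecast, not something the protocol states.
- **Double counting over two 12-month windows.** The first report's window runs from country launch in 2016 to 31 March 2019. That postponed data would be merged is an inference. Section 9.2 aims to avoid the same physicians each year and 9.6 allows for removing duplicates. Some risk remains: 9.2 concedes that physicians may overlap, and no method is given for spotting a de-identified patient across years.

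**Conclusion.** The concern holds as an inconsistency between the stated precision, the operating target and the shortfall rule. The plan accepts as on target sample sizes whose worst-case half-width is up to ±13.9 points against a stated ±10. The figures use the protocol's own formula, with p = 50% and independent records. The postponement option contradicts the annual reporting commitment and cannot be used after the final survey. Severity is should-fix: no hypothesis test is affected, but the precision claim is wrong for most of the permitted range and reporting is left to annual discretion.

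**What to change.** 1. Reconcile 4.8, 9.2, 9.5.1, 9.5.2 and 9.6.1 to one target and one explicit stopping number: for example, aim for 100 and do not stop at 50.
2. Replace the wording in 9.5.2 that makes 100 a required minimum with the precision the range gives: about ±14 points at 50 and ±10 at 100 for a proportion of 50%, before clustering, with zero-event upper limits of 7.1% and 3.6%.
3. Replace the case-by-case agreement and the yearly feasibility check with a fixed rule: every country is reported every year with the records obtained and their confidence intervals. Pooling across years appears only as an additional table, with a note that patients may recur.

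Keeping 100 as the goal and labelling 50 a feasibility floor would also reconcile the text, provided the stopping number and the precision at 50 are stated. The cost is wording only: a less favourable stated precision and some annual country tables with wide intervals.
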